5.8.1.2 Dose Modification

DOSMOD01

	ARM A (N=xxx)
Overall	
n	xxx
Number of patients with a dose modification	xx (xx%)
Type of modification	
n	xxx
Infusion Stopped and Restarted at the same rate	xx (xx%)
Infusion Stopped and Restarted at a lower rate	xx (xx%)
Prematurely Stopped and Not Restarted	xx (xx%)
Reason for modification	
n	xxx
Adverse Event	xx (xx%)
Other	xx (xx%)
xxxxxxxxxxxxxx	xx (xx%)
Cycle 1 Day 1	
n	xxx
Number of patients with a dose modification	xx (xx%)

...
 n is the number of patients who experienced a dose modification at the corresponding visit.

Listing 8 MEDL01

CRTN/Pt. No.	Clinical Planned Event	From	To	Durati on days hh:mm	TT be g da y	Actual Dose (mg)	Cumulat ive Dose (mg)	Treatmen t Modifica tion	Reason for Modific ation
xxxxxxx/xxx x									
BENDAMUS TINE	C1D1	ddmmmyyyy hh:mm:ss	ddmmmyyyy hh:mm:ss	x hh:mm	xx	xx.x	xx.x	xxxxxxxxx xx	xxxxxxxx xxx
	C2D1	ddmmmyyyy hh:mm:ss	ddmmmyyyy hh:mm:ss	x hh:mm	xx	xx.x	xx.x	xxxxxxxxx xx	xxxxxxxx xxx
	C3D1	ddmmmyyyy hh:mm:ss	ddmmmyyyy hh:mm:ss	x hh:mm	xx	xx.x	xx.x	xxxxxxxxx xx	xxxxxxxx xxx
	...								
OBINUTUZ UMAB	C1D1	ddmmmyyyy hh:mm:ss	ddmmmyyyy hh:mm:ss	x hh:mm	xx	xx.x	xx.x	xxxxxxxxx xx	xxxxxxxx xxx
	C1D8	ddmmmyyyy hh:mm:ss	ddmmmyyyy hh:mm:ss	x hh:mm	xx	xx.x	xx.x	xxxxxxxxx xx	xxxxxxxx xxx
	C1D15	ddmmmyyyy hh:mm:ss	ddmmmyyyy hh:mm:ss	x hh:mm	xx	xx.x	xx.x	xxxxxxxxx xx	xxxxxxxx xxx
	...								
...									

CRTN = Clinical Research Task Number (center no.).
 C = Cycle, D = Day.
 '?' = Duration could not be calculated.
 TT = Trial Treatment.

5.8.2 Adverse Events

An Adverse Event (AE) is any untoward medical occurrence in a study. A Serious Adverse Event (SAE) will be summarized as per the data collected.

Alongside seriousness, also severity (intensity of an AE graded by NCI-CTCAE) and causality (relation to study drug) are reported for each AE.

5.8.2.1 Adverse Events of Special Interest

Adverse events of special interest were defined in accordance with Idasanutlins's mode of action:

- Cases of potential drug-induced liver injury that include an elevated ALT or AST in combination with either an elevated bilirubin or clinical jaundice, as defined by Hy's Law (see Section 5.3.5.6)
- Suspected transmission of an infectious agent by the study drug, as defined below Any organism, virus, or infectious particle (e.g., prion protein transmitting transmissible spongiform encephalopathy), pathogenic or non-pathogenic, is considered an infectious agent. A transmission of an infectious agent may be suspected from clinical symptoms or laboratory findings that indicate an infection in a patient exposed to a medicinal product. This term applies only when a contamination of the study drug is suspected.
- TLS (clinical TLS per Howard criteria, see Appendix 4)
- Bleeding if associated with Grade ≥ 3 thrombocytopenia
- Grade ≥ 3 febrile neutropenia

- Grade \geq 2 diarrhea
- Grade \geq 2 C. difficile infection

No summaries are produced for AESI but listing for AESI will be produced. However, they are included in Safety summary (AET01_02). See template for more details.

5.8.2.2 *Adverse event reporting*

A flag will indicate to which study phase an AE belongs to: before therapy, treatment period on, or follow up (general section 3.1.1).

AE Toxicity grading will be based on the **NCI-CTC** grading system

All AEs are assigned to a study phase based on the imputed AE start date. AEs which start before study day 1 belong to the before therapy period (i.e PRIOR). AEs during treatment period are all AEs which started on or after Study Day 1. The start of follow-up is after the study completion / early termination visit. In the unlikely scenario of a missing imputed AE start date the AE is assigned to the study phase.

Please note: The Roche standard rules are applied to impute the AE start date, which means that the imputed AE start date can only be missing if the date of study day 1 (TRTSDTM) is missing. Please refer to

https://gdsr.roche.com/resource/gdsr.roche.com/release/products/dataAnalysis/Global_Data_Analysis_Standards_Safety.xls for more details on the imputation rules.

Importantly, each AE can belong to only one time period.

All treated patients will be analyzed by descriptive summaries of the AEs by System Organ Class mapped term (by descending frequency) and by Preferred Term (by descending frequency).

Summaries will report all AEs which occurred on or after Study Day 1. In addition, AEs which start during follow up will be summarized in a separate single table if a sufficient number of patients will have entered follow-up. Multiple occurrences of the same AE (by PT) per subject are counted only once unless defined otherwise. For Total number of events, multiple occurrences of the same AE on an individual are counted separately. A separate table is produced for adverse events with incidence rate of more than 10% and 5% (AET02_01).

For some specific adverse event types, additional tables will display instances where multiple occurrences of the same AE in the same patient are all counted (EUDRAT01, EUDRAT02).

Summaries of AEs by Grade will be generated for each population – patients with splenomegaly, without and all rux naïve patients (AET04_01).

A standard summary table is produced for AEs falling into SMQ-hemorrhage (wide).

Listings will include all reported AEs and will include a flag to indicate the study period (AEL02_02, AEL02_03, AEL02_04, AEL03_01).

Deaths are AEs with fatal outcomes and will be presented in a separate listing (AEL04_02) and table (AET07_01).

A glossary of all adverse event coded terms will be provided (AEL01_NOLLT)

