8.2 SAFETY ASSESSMENTS

Safety assessments will consist of monitoring and recording AE, including serious adverse events and non-serious adverse events of special interest, performing protocol-specified safety laboratory assessments, measuring protocol-specified vital signs, and conducting other protocol-specified tests that are deemed critical to the safety evaluation of the study.

ECG testing will be monitored at baseline and on treatment as outlined in Section 1.2 and in Section 8.2.3. ECG monitoring will be performed locally to mitigate the potential risk for idasanutlin of supraventricular arrhythmias. In case of emergence of supraventricular arrhythmias the Sponsor needs to be immediately notified as this represents an adverse event of special interest for this protocol Section 8.3.6.

Certain types of events require immediate reporting to the Sponsor, as outlined in Section 8.3.5.2. Planned timepoints for all safety assessments are provided in the SoA (Section 1.2).

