8.3.7 Non-Serious Adverse Events of Special Interest

Adverse events of special interest are required to be reported by the Investigator to the Sponsor immediately (i.e., no more than 24 hours after learning of the event; see [Appendix 10](#) for reporting instructions).

Adverse events of special interest for this study include the following:

- Cases of an elevated ALT or AST in combination with either an elevated bilirubin or clinical jaundice, as defined in [Appendix 11](#).
- Suspected transmission of an infectious agent by the study treatment, as defined below:
 - Any organism, virus, or infectious particle (e.g., prion protein transmitting transmissible spongiform encephalopathy), pathogenic or non-pathogenic, is considered an infectious agent. A transmission of an infectious agent may be suspected from clinical symptoms or laboratory findings that indicate an infection in a patient exposed to a medicinal product. This term applies only when a contamination of the study treatment is suspected.
- Thromboembolic events (Grade ≥ 2) are of particular interest for the PV population and should be reported to the Sponsor.
- Grade 3 or 4 (or any grade in presence of bleeding) thrombocytopenia (refer to [Appendix 12](#) for a list of example Preferred Terms considered pertinent to thrombocytopenia)
- Grade ≥ 3 systemic infection;
- Grade ≥ 3 GI toxicity (refer to [Appendix 12](#) for the list of PT considered pertinent to GI toxicity);
- Any grade supraventricular arrhythmias (MedDRA PT reported included in the Supraventricular tachyarrhythmias (refer to [Appendix 12](#) for a list of example Preferred Terms considered pertinent to Supraventricular tachyarrhythmias).

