¹ All events of ALT $\geq 3 \times$ upper limit of normal (ULN) and bilirubin $\geq 2 \times$ ULN (>35% direct bilirubin) or ALT $\geq 3 \times$ ULN and international normalized ratio (INR) > 1.5, if INR measured which may indicate severe liver injury (possible Hy's Law), must be reported as an SAE (excluding studies of hepatic impairment or cirrhosis).

² Local urine testing will be standard for the protocol unless serum testing is required by local regulation or IRB/IEC.

Investigators must document their review of each laboratory safety report.

Additional statistical considerations for Clinical Laboratory Data

Standard Reference Ranges and Transformation of Data

Roche standard reference ranges, rather than the reference ranges of the Investigator, will be used for all parameters. For most parameters, the measured laboratory test result will be assessed directly using the Roche standard reference range. Certain laboratory parameters will be transformed to Roche's standard reference ranges.

A transformation will be performed on certain laboratory tests that lack sufficiently common procedures and have a wide range of Investigator ranges, e.g., enzyme tests that include AST, ALT, and alkaline phosphatase and total bilirubin. Since the standard reference ranges for these parameters have a lower limit of zero, only the upper limits of the ranges will be used in transforming the data.

Definition of Laboratory Abnormalities

For all laboratory parameters included, there exists a Roche predefined standard reference range. Laboratory values falling outside this standard reference range will be labeled "H" for high or "L" for low in participant listings of laboratory data.

In addition to the standard reference range, a marked reference range has been predefined by Roche for each laboratory parameter. The marked reference range is broader than the standard reference range. Values falling outside the marked reference range that also represent a defined change from baseline will be considered marked laboratory abnormalities (i.e., potentially clinically relevant). If a baseline value is not available for a participant, the midpoint of the standard reference range will be used as the participant's baseline value for the purposes of determining marked laboratory abnormalities. Marked laboratory abnormalities will be labeled in the participant listings as "HH" for very high or "LL" for very low.

Appendix 10

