It is the Investigator's responsibility to review all vital sign findings. Medical and scientific judgment should be exercised in deciding whether an isolated vital sign abnormality should be classified as an adverse event.

If a clinically significant vital sign abnormality is a sign of a disease or syndrome (e.g., high blood pressure), only the diagnosis (i.e., hypertension) should be recorded on the Adverse Event eCRF.

Observations of the same clinically significant vital sign abnormality from visit to visit should not be repeatedly recorded on the Adverse Event eCRF, unless the etiology changes. The initial severity of the event should be recorded, and the severity or seriousness should be updated any time the event worsens.

6. Abnormal Liver Function Tests

Idasanutlin has hepatic toxicity as a potential risk. Accordingly, ALT, AST and bilirubin will be monitored throughout the trial as specified in Section 1.2. Patients with active hepatitis will be not eligible for treatment (see Exclusion Criteria Section 5.2). Patients at screening must also have adequate hepatic function. In the case of an abnormal liver function test on trial, participants will be managed as described in Section 8.3.9.

The finding of an elevated ALT or AST ($> 3 \times \text{ULN}$) in combination with either an elevated total bilirubin ($> 2 \times \text{ULN}$) or clinical jaundice in the absence of cholestasis or other causes of hyperbilirubinemia is considered to be an indicator of severe liver injury. Therefore, investigators must report as an adverse event the occurrence of either of the following:

- Treatment-emergent ALT or AST $> 3 \times \text{ULN}$ in combination with total bilirubin $> 2 \times \text{ULN}$.
- Treatment-emergent ALT or AST $> 3 \times \text{ULN}$ in combination with clinical jaundice.

The most appropriate diagnosis or (if a diagnosis cannot be established) the abnormal laboratory values should be recorded on the Adverse Event eCRF and reported to the Sponsor immediately (i.e., no more than 24 hours after learning of the event), either as a serious adverse event or a non-serious adverse event of special interest.

7. Overdose

Any study treatment overdose, or incorrect administration of study treatment, should be noted on the Study Treatment Administration eCRF.

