13. Post-Study Adverse Events and Serious Adverse Events

If the Investigator becomes aware of any other serious adverse event occurring after the end of the adverse event reporting period, if the event is believed to be related to prior study drug treatment the event should be reported directly to the Sponsor or its designee, either by faxing or by scanning and emailing the Serious Adverse Event Reporting Form using the fax number or email address provided to investigators.

14. Reporting Requirements for Serious Adverse Events and Non-Serious Adverse Events of Special Interest

Events That Occur prior to Study Drug Initiation

After informed consent has been obtained but prior to initiation of study drug, only serious adverse events caused by a protocol-mandated intervention should be reported. The Serious Adverse Event/Adverse Event of Special Interest Reporting Form provided to Investigators should be completed and submitted to the Serious Adverse Event Responsible immediately (i.e., no more than 24 hours after learning of the event).

Events That Occur after Study Drug Initiation

For reports of serious adverse events and non-serious adverse events of special interest (see Sections 8.3.5 and 8.3.6) that occur after initiation of study drug, investigators should record all case details that can be gathered immediately (i.e., within 24 hours after learning of the event) on the appropriate Adverse Event of Special Interest/ Serious Adverse Event eCRF form and submit the report via the electronic data capture (EDC) system. A report will be generated and sent to the Sponsor's Safety Risk Management department.

In the event that the EDC system is unavailable, the Serious Adverse Event/Adverse Event of Special Interest Reporting Form provided to investigators should be completed and submitted to the Serious Adverse Event Responsible immediately (i.e., no more than 24 hours after learning of the event).

Once the EDC system is available, all information will need to be entered and submitted via the EDC system.

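### The SAP's list of adverse events of special interest is not the protocol's: of seven protocol categories, three are absent, two are redefined and one has no usable cut-off

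*SAP*

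**What the plan says.** Protocol 8.3.7 lists seven AESI categories for immediate reporting. Thromboembolic events of Grade 2 or higher "are of particular interest for the PV population and should be reported to the Sponsor". Thrombocytopenia is entered as "Grade 3 or 4 (or any grade in presence of bleeding) thrombocytopenia". Arrhythmia is entered as "Any grade supraventricular arrhythmias (MedDRA PT reported included in the Supraventricular tachyarrhythmias", and protocol 8.2 repeats that the Sponsor must be told at once of a supraventricular arrhythmia, "as this represents an adverse event of special interest for this protocol". The other four are liver injury (defined in Appendix 11), suspected transmission of an infectious agent, systemic infection of Grade 3 or higher, and gastrointestinal toxicity of Grade 3 or higher on the Appendix 12 terms. Under Appendix 11 item 14, sites record AESIs on a dedicated AESI/SAE form "and submit the report via the electronic data capture (EDC) system".

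SAP 5.8.2.1 has its own seven items: liver injury by Hy's Law (citing a Section 5.3.5.6), infectious-agent transmission, "TLS (clinical TLS per Howard criteria, see Appendix 4"), bleeding with Grade 3 or higher thrombocytopenia, febrile neutropenia of Grade 3 or higher, diarrhea of Grade 2 or higher, and C. difficile infection of Grade 2 or higher. It plans an AESI listing (shell AEL02_06) and AESI rows in the safety summary AET01_02. A note under AET01_02 says that AESIs are identified by the rules of the SAP's AESI section.

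**The concern.** Two documents for one trial use the same label for different sets of events. Sites report under the protocol list, while AET01_02 is built from the SAP list, so the reported AESIs and the tabulated AESIs would not agree. The missing categories include one that the protocol singles out for this disease (thromboembolic events) and one for which it sets up ECG monitoring (supraventricular arrhythmia). A reader of the safety summary would see no AESI row for either and could take that to mean that none occurred.

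The cross-references suggest text carried over from other studies. That is an inference; the contradiction does not depend on it.

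**Working it through.** No sample-size, power or event figure is involved. The check sets the two lists side by side.

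| Protocol 8.3.7 | SAP 5.8.2.1 | Result |
|---|---|---|
| Suspected transmission of an infectious agent | Same | Full match |
| Liver: ALT or AST with bilirubin or jaundice, per Appendix 11 | Same structure, by Hy's Law, Section 5.3.5.6 | Category level only |
| Thrombocytopenia: Grade 3–4, or any grade with bleeding | Bleeding with Grade ≥3 thrombocytopenia | Redefined |
| GI toxicity: Grade ≥3, Appendix 12 terms | Diarrhea only, Grade ≥2 | Redefined |
| Thromboembolic events, Grade ≥2 | None | Absent |
| Systemic infection, Grade ≥3 | None | Absent |
| Supraventricular arrhythmia, any grade | None | Absent |

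Protocol tally: 1 full + 1 category level + 2 redefined + 3 absent = 7. In the other direction, 7 − 1 − 1 − 2 = 3 SAP items have no protocol counterpart: tumor lysis syndrome (TLS), febrile neutropenia and C. difficile infection. Protocol 8.3.9 names the first two as identified risks at higher doses, but 8.3.7 does not make them AESIs.

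**Liver.** Protocol Appendix 11 item 6 uses ALT or AST >3×ULN with total bilirubin >2×ULN or clinical jaundice; this combination "in the absence of cholestasis or other causes of hyperbilirubinemia is considered to be an indicator of severe liver injury". Section 5.3.5.6 exists in neither document. The only supplied protocol text that names Hy's Law is footnote 1 of Appendix 9. Its rule is ALT ≥3×ULN with bilirubin ≥2×ULN (>35% direct), or ALT ≥3×ULN with INR >1.5, "which may indicate severe liver injury (possible Hy's Law), must be reported as an SAE". That rule has no AST arm and no jaundice arm. The SAP therefore gives no cut-off that can be programmed.

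**Thrombocytopenia.** The protocol takes a union (Grade 3–4, or bleeding at any grade) and the SAP takes an intersection (bleeding and Grade ≥3). Grade 3–4 without bleeding and Grade 1–2 with bleeding both drop out.

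**GI toxicity.** Appendix 12 gives 33 example terms. Protocol 6.1.1 names 6 main GI events from Phase I: nausea, diarrhea, vomiting, abdominal pain, constipation and anorexia. All but anorexia are Appendix 12 terms, which leaves 5. The SAP keeps 1 (diarrhea) and drops 5 − 1 = 4. No Grade ≥3 diarrhea is lost, because the SAP cut-off is lower, but Grade 2 diarrhea is added.

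**Supraventricular arrhythmia.** The whole SMQ, with 10 example terms in Appendix 12, is dropped.

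**Other dead references.** The TLS item cites Appendix 4. The SAP has only appendices 6.1 and 6.2, and protocol Appendix 4 is the WHO diagnostic criteria. The AET01_02 note cites a thrombotic microangiopathy definition at Point 5 of the AESI section, where the fifth item is febrile neutropenia.

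**The case against.** The strongest reply is that little is lost. No primary endpoint or decision rule uses AESIs, and protocol 9.4.3 does not require an AESI table. Every reported event stays in the listings and in the general adverse event tables. Grade ≥3 events, serious events and the hemorrhage SMQ have their own outputs, and laboratory shift tables are planned, with platelets on the parameter list. All of this stands and limits the severity.

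It is also fair that AET01_02 would not be empty of protocol AESIs: transmission cases, liver cases in some form, Grade ≥3 diarrhea, and bleeding with Grade ≥3 thrombocytopenia would appear. The fault lies in the set as a whole.

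On liver, the SAP wording follows protocol 8.3.7 closely, so Appendix 11 is the natural reading. What remains is a dead pointer and no stated cut-off. That is why it is counted as a category-level match.

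AEL02_06 has no selection rule in its shell. If it were drawn from the AESI eCRF form it would follow the protocol, and then the listing and AET01_02 would disagree with each other.

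Febrile neutropenia does appear in Appendix 12, whose title refers to AESIs, but under the leukopenia terms. Protocol 8.3.9.2 uses those for a discontinuation rule, and 8.3.7 does not list the event.

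None of this reconciles the two lists, and the SAP gives no reason for departing from 8.3.7 beyond a general reference to mode of action.

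**Conclusion.** The concern holds. Followed as written, the SAP would fill the AESI rows of AET01_02 with a set that leaves out three of the seven protocol categories, changes two, leaves one without a cut-off and adds three of its own. It should be fixed, but it does not threaten the trial's efficacy conclusions.

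The loss is a grouped AESI count. It matters most for non-serious Grade 2 thromboembolic events and non-serious Grade 1–2 supraventricular arrhythmias, which the Grade ≥3 and SAE outputs would not pick up, and for the link between bleeding and thrombocytopenia below Grade 3.

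The figures above count categories and terms, not events; the documents give no basis for an event count. The conclusion for AET01_02 rests on the note under its shell. The conclusion for AEL02_06 rests on the assumption that it uses the same rules. The separate List of Planned Outputs is not among the documents.

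**What to change.** In SAP 5.8.2.1:

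- Replace the list with the seven protocol 8.3.7 categories and thresholds, give each a row in AET01_02, and derive AEL02_06 from the same rules.
- Point the liver item to protocol Appendix 11.
- Define GI toxicity, supraventricular tachyarrhythmia and thrombocytopenia by the narrow SMQs named in Appendix 12, in the MedDRA version used for reporting, not by the example terms alone.
- Specify term sets for thromboembolic events and systemic infection, for which Appendix 12 gives none.
- For thrombocytopenia with bleeding, specify the bleeding terms (for example the hemorrhage SMQ already planned in SAP 5.8.2.2) and a linkage rule (for example, the two events overlap by at least one day).
- Delete the microangiopathy note and the dead cross-references.
- If TLS, febrile neutropenia, Grade ≥2 diarrhea and C. difficile infection are still wanted, show them as separately labelled selected events, not as protocol AESIs.

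Fix these rules before database closure. The cost is SAP text, three term sets (thromboembolic events, systemic infection, bleeding), one linkage rule and shell programming. No protocol or CRF change is needed.

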
 To evaluate the safety of idasanutlin monotherapy in patients with HU resistant/intolerant PV and ruxolitinib resistant/intolerant patients 	
 Clinical safety laboratory tests (hematology, clinical chemistry, urinalysis, pregnancy testing) Incidence, nature and severity of AEs graded according to the NCI CTCAE v4.0 Incidence and severity of AEs, including targeted AEs. ECOG PS, ECG, vital signs Concomitant medication

 To characterize the pharmacokinetic (PK) parameters of idasanutlin and M4 metabolite in patients with HU resistant/intolerant PV 	
 C_{max}, C_{trough}, t_{max}, CL, CL/F, Vd_{ss}, AUC, $t_{1/2}$, and potentially other parameters derived.

 To evaluate the effect of treatment with idasanutlin on the symptoms of PV, physical functioning, general health status/HRQoL, and change in condition in all enrolled patients, as well as in those with and without baseline splenomegaly 	
 Mean and mean change from baseline to each assessment: 
 MPN symptom assessment form total symptom score (MPN-SAF TSS) European Organization for Research and Treatment of Cancer Quality of Life Questionnaire–Core 30 (EORTC QLQ-C30) Distribution of responses at each assessment and across time: 
 Patient Global Impression of Change scale

All Patients, Irrespective of Prior Ruxolitinib Exposure:

Objectives	Endpoints
Secondary	

 To evaluate the safety of idasanutlin monotherapy in patients with HU resistant/intolerant PV irrespective of ruxolitinib exposure (all patients) 	
 Clinical safety laboratory tests (hematology, clinical chemistry, urinalysis, pregnancy testing) Incidence, nature and severity of AEs graded according to the NCI CTCAE v4.0 Incidence and severity of AEs, including targeted AEs. ECOG PS, ECG, vital signs Concomitant medication
Tertiary/Exploratory	

 To assess the relationship between PK exposure and clinical responses, including AEs 	
 Concentration-time profiles following administration of idasanutlin or derived (or modeled/simulated) parameters will be correlated with clinical endpoints including PD and AEs

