3. FILTERS, POPULATIONS AND SUBGROUPS

Filter Category	Label of population or subgroup	Filter	Description
Main Populations	Safety-Evaluable Patients	SE	All patients who received at least one dose of the study treatment, whether prematurely withdrawn from the study or not, will be included in the safety analysis.
	Intent-to-Treat Patients	IT	All enrolled patients, regardless of previous ruxolitinib treatment
	Primary Efficacy Patients	PE	Ruxolitinib-naive patients both with splenomegaly by imaging or without splenomegaly who have Completed at least 32 weeks of treatment or withdrew prior to Week 32 due to NR or progressive disease.
	Early-Look Efficacy Patients	ELE	Patients who have completed at least 3 and/or 5 cycles

	PK Patients	PK	All patients who have received at least one dose of study treatment and who have data from at least one post-dose sample will be included in the PK analysis population. Patients will be excluded from the PK analysis population if they significantly violate the inclusion or exclusion criteria, deviate significantly from the protocol, or if data are unavailable or incomplete which may influence the PK analysis. Excluded cases will be documented together with the reason for exclusion. All decisions on exclusions from the analysis will be made prior to database closure.
	Pharmacodynamic Patients	PD	All patients who had at least one pre-dose and one post-dose pharmacodynamic assessment will be included and analyzed.
	Prior Rux exposed patients	RUX	
	Patients with splenomegally	SPLNML	All patients with splenomegaly
	Patients without splenomegally	WOSPLML	
	All Rux naïve	RUXNAIVE	
Sub-setting of data by patient characteristics – key subgroups only	Patients aged >= 65	AGEGE65	Patients aged 65 or more

Additional filters are used to subset data based on assessments, e.g. serious adverse events or assessments during treatment.

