5.1 General output set up

The key layout will be driven by the populations.

Wherever possible the tables will be split by Ruxolitinib exposure and splenomegaly status at baseline. The table header would look like follows:

	Ruxolitinib Naive		Ruxolitinib Exposed			All
Patients (N=XX)	(N=XX)		(N=XX)			

With Splenomegaly Patients (N=XX)	Without Splenomegaly (N=XX)	All Patients (N=XX)	With Splenomegaly (N=XX)	Without Splenomegaly (N=XX)	All Patients (N=XX)	All
--	-----------------------------------	---------------------------	--------------------------------	-----------------------------------	---------------------------	-----

Listings will be grouped in a similar way.

As a general statement, the outputs will include the name of the associated population e.g. “Safety-Evaluable Patients”. Listings will generally include all patients of the relevant population.

Some outputs may be produced for specified populations only. For a detailed list of outputs please see the List of Planned Outputs (LoPO).

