Note: "Thrombotic microangiopathy" is based on the TMA definition in Point 5 of the Adverse Event of Special Interest section
All Adverse Events of Special Interest are identified using the rules defined in "Adverse Event of Special Interest" section..

AET02_01: Adverse Events by System Organ Class and Preferred Term

Adverse Events: <Specify Population>

Protocol: xxxnnnn

	Group1
	(N=xx)

ALL BODY SYSTEMS	
Total pts with any AE	xx (xx.x%)
Total number of AEs	xx
SOC 1	
Total pts with any AE	xx (xx.x%)
Preferred term 1	xx (xx.x%)
Preferred term 2	xx (xx.x%)
Preferred term 3	xx (xx.x%)
Preferred term 4	xx (xx.x%)
...	xx (xx.x%)
Total number of AEs	xx
SOC 2	
Total pts with any AE	xx (xx.x%)
Preferred term 1	xx (xx.x%)
Preferred term 2	xx (xx.x%)
Preferred term 3	xx (xx.x%)
Preferred term 4	xx (xx.x%)
...	xx (xx.x%)
Total number of AEs	xx

Investigator text for AEs encoded using MedDRA version xx.x. Percentages are based on N in the column headings.

For frequency counts by preferred term, multiple occurrences of the same AE in an individual are counted only once. For frequency counts of "Total number of events" rows, multiple occurrences of the same AE in an individual are counted separately.

AET04: Adverse Events by Highest NCI-CTCAE Grade

Adverse Events by Highest CTC Grade

Protocol: xxxnnnn

Population: xxx

MedDRA System Organ Class MedDRA Preferred Term	Grade (0)	Total (N=nnn ¹)
- Any adverse events -	- Any Grade -	nn ² (xx.x ³ %)
	1	nn ⁴ (xx.x%)
	2	nn (xx.x%)
	3	nn (xx.x%)
	4	nn (xx.x%)
	5	nn (xx.x%)
BLOOD AND LYMPHATIC SYSTEM DISORDERS		
- Overall -	- Any Grade -	nn ⁵ (xx.x%)
	1	nn ⁶ (xx.x%)
	2	nn (xx.x%)
	3	nn (xx.x%)
	4	nn (xx.x%)
	5	nn (xx.x%)
NEUTROPENIAS	- Any Grade -	nn ⁷ (xx.x%)
	1	nn ⁸ (xx.x%)
	2	nn (xx.x%)
	3	nn (xx.x%)
	4	nn (xx.x%)
	5	nn (xx.x%)

Investigator text for AEs encoded using MedDRA version xx.x. Percentages are based on N in the column headings.

All counts represent patients. Multiple occurrences of the same AE in one individual are counted once at the highest grade for this patient.

To the SOC Overall row counts, a patient contributes only with the AE occurring with the highest grade within the SOC.

(0) Grade: 1 = mild; 2 = moderate; 3 = severe; 4 = life threatening.

Similarly Summary of Adverse Events with NCI-CTCAE Grade >=3 table, Listing of Adverse Events with Most Severe NCI-CTCAE Grade >= 3 and Summary of Adverse Events Leading to Dose Interruption will be provided.

AET07_01 Adverse Events Resulting in Death

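### SAP 5.8.2.2 leaves ruxolitinib-resistant/intolerant patients and the all-patient set off its list for the AE-by-grade table, so a separate severity table for that cohort is not assured

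*SAP*

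**What the plan says.** SAP 5.8.2.2 (Adverse event reporting) plans the AE summaries by grade for a stated list of populations: "patients with splenomegaly, without and all rux naïve patients (AET04_01". No other population is named for this table.

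The protocol synopsis and Table 3 give the resistant/intolerant cohort its own secondary safety objective: "To evaluate the safety of idasanutlin monotherapy in patients with HU resistant/intolerant PV and ruxolitinib resistant/intolerant patients". Its endpoints include the incidence, nature and severity of AEs by CTCAE v4.0 grade. The same endpoint is set for ruxolitinib-naive patients and, separately, for all patients whatever their ruxolitinib history. Protocol Table 10 (Section 9.3) calls for analyses within each population and combined, and Table 11 (Section 9.4.3) includes AE severity in the safety analyses.

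The general rule in SAP 5.1 reads: "Wherever possible the tables will be split by Ruxolitinib exposure and splenomegaly status at baseline". Its model header has ruxolitinib-exposed columns (with splenomegaly, without, all) and an all-patients column. The same section adds "Some outputs may be produced for specified populations only" and refers to the LoPO for detail. SAP Section 3 contains a RUX filter, labelled "Prior Rux exposed patients" and given no description, and describes the splenomegaly filter as "All patients with splenomegaly".

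**The concern.** The two documents name different sets for the same endpoint. The SAP presents its output specifications as detailed enough for a programmer to implement. A programmer who follows 5.8.2.2 to the letter tabulates severity by system organ class and preferred term for the naive cohort and not for the resistant/intolerant cohort.

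The omitted cohort matters because protocol Section 4.1 gives its expansion the purpose of registration and makes it depend on a clear positive benefit/risk signal. Section 9.2.2 says the totality of efficacy and safety data would be considered. Harms should therefore be tabulated in the same way for the two cohorts that the SAP displays side by side.

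**Working it through.** No arithmetic decides this point, and the plan has no figure to reproduce. The check is a comparison of texts.

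1. Sets named for AE severity:

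| Source | Rux-naive | Rux-resistant/intolerant | All patients |
|---|---|---|---|
| Protocol synopsis and Table 3 | yes | yes | yes |
| SAP 5.1 model header | yes | yes (exposed) | yes |
| SAP 5.8.2.2, AET04_01 | yes | not named | not named |
| AET04 shell | open | open | open |
| Grade >=3 table and listing | not stated | not stated | not stated |

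2. What the two splenomegaly groups in 5.8.2.2 mean for exposed patients:
- If they follow the Section 3 filter, which is not restricted to naive patients, exposed patients enter the by-grade tables, but pooled with naive patients.
- If they follow SAP 5.7.2.1 and 5.7.2.2, where the same trio is defined among ruxolitinib-naive patients, exposed patients are left out.
- Under neither reading does the sentence itself name a separate exposed table.

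3. Does the shell settle it? The AET04 shell has a single total column and the placeholder "Population: xxx". That suits one table per population, with the populations supplied from elsewhere, and 5.8.2.2 is where they are named. The shell neither excludes nor secures the exposed cohort.

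4. What the other planned outputs show about severity:
- The safety summary AET01_02 has one row counting patients with a Grade >=3 event.
- The Grade >=3 table and listing are introduced directly after AET04 as similar outputs, with no population of their own.
- AE listings show the most extreme grade of each event.
- The SOC and preferred-term summaries cover all treated patients but carry no grade.

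   A Grade >=3 table omits Grades 1 and 2. Protocol Section 2.3 shows why that can matter. In the earlier study in PV and essential thrombocythemia (12 patients at 100 mg or 150 mg) there were 21 nausea and 22 diarrhea events, 21 + 22 = 43, and all were Grade 1 or 2. Events like these would appear by grade only in AET04 and the listings.

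5. Size of the cohort concerned (protocol Section 9.2.2): about 20 efficacy-evaluable patients in the initial phase, and 20 + 40 = 60 if the expansion opens.

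**The case against.** A reader might infer that the SAP restricts by-grade reporting to the named groups and that the resistant/intolerant cohort gets no such table. The case against that reading is good.

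- The SAP elsewhere names only naive populations in its prose and still prints exposed columns. SAP 5.7.1 lists three naive populations, yet its response shell has exposed and all-patient columns. SAP 5.7.2.2 refers to the three naive populations, and its table has exposed columns too. A naive-only list in this SAP is weak evidence that exposed columns are dropped.
- Nothing makes the 5.1 split impossible for AET04, and that header nests splenomegaly within exposure, so exposed patients need not be pooled with naive ones.
- The LoPO is the SAP's full list of outputs and is not among the documents. Absence of the table cannot be established without it.
- Grade >=3 outputs and per-event listings carry no population limit.

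All of this stands, and it rules out the stronger reading. It does not remove the conflict. SAP 5.1 also allows outputs for specified populations, and 5.8.2.2 does specify them. Unlike the two efficacy sections, the AET04 shell prints no exposed columns. SAP 5.7.2.4 and 5.7.2.5 add all-patient and exposed analyses for efficacy, with no counterpart for AEs by grade. Listings show individual grades but do not summarize an endpoint.

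**Conclusion.** The point holds as an inconsistency: the list in SAP 5.8.2.2 does not match the protocol's three safety sets or the SAP 5.1 default. A separate by-grade table for about 20 patients (about 60 after expansion) is not assured as the text stands.

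Two further inferences should be resisted. First, a reader might express the gap as a share of patients: 20/(20 + 20) = 50% initially and 60/(20 + 60) = 75% with the expansion. These only restate cohort sizes, and they assume 20 naive patients. With the 40 the protocol allows, they become 20/(40 + 20) = 33% and 60/(40 + 60) = 60%. They measure neither bias nor lost information. Second, a reader might infer that the expansion decision turns on AET04. The stated numerical condition is Hct control above 30%, alongside the totality of data and the sponsor's discretion; nothing ties it to this table.

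The conclusion assumes that the SAP's exposed group is the protocol's resistant/intolerant cohort. The eligibility criteria support this, since previously exposed patients must be resistant or intolerant to enter. It also assumes that the LoPO has not already settled the matter. The effect is on the completeness of safety reporting, not on any efficacy estimate.

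**What to change.** In SAP 5.8.2.2, replace the population list for AET04_01 with ruxolitinib-naive, ruxolitinib-resistant/intolerant (the existing RUX filter) and all safety-evaluable patients. State that the 5.1 column header applies, with splenomegaly shown within cohort. Give the Grade >=3 table the same populations explicitly, and align the LoPO.

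The cost is one amended sentence and added columns in an existing table program, with no new data. The drawback is sparse cells: once a cohort of about 20 is split by splenomegaly and by grade within preferred term, many counts will be zero or one. Those columns should be read descriptively, in keeping with the rest of the plan.
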